5.2. Study Design

Under the 2016 Kenya PrEP guidelines,¹⁷⁷ all persons initiating PrEP undergo clinical assessment to ask about symptoms of acute HIV infection, receive rapid HIV-1 and creatinine testing (estimated creatinine clearance >60 mL/min is required to start PrEP), and adherence counseling.

Patients who qualify for and initiate PrEP are subsequently seen in 1 month, in 3 months, and then every 3 months for repeat HIV testing, continued risk assessment, and adherence counseling for daily PrEP under the standard of care (SOC). For this pilot RCT, we will recruit women ≥18 years old on PrEP at Thika at the visit that occurs 3 months after PrEP initiation (per the 2016 Kenya PrEP guidelines). Patients will be enrolled and randomized in a 1:1 fashion at that visit

(month 0 or baseline visit of study) using sealed opaque envelopes to the intervention arm versus the SOC arm (**Figure 7**). A minimum of 100 and not exceeding 120 women will be recruited, with about 50 - 60 randomized to the intervention arm and about 50 - 60 to the SOC arm (**Figure 7**). We anticipate that randomizing established patients (at their second PrEP follow up visit since PrEP visits are to occur 1 and 3 months after PrEP initiation per Kenya guidelines) will minimize attrition during the study.

Upon randomization, study visits will occur at 0 (baseline visit), 3, 6, 9 and 12 months after study enrollment. Each visit will include rapid testing for HIV, pregnancy testing if the participants requests it or is unsure of being pregnant (per standard of care), and creatinine measurement (per 2016 Kenya PrEP guidelines), as well as adherence counseling. As per the 2016 Kenya PrEP guidelines, any other laboratory testing or assessments will be performed per the history and physical examination. Self-reported time since last PrEP dose taken will be collected via a visual analog scale, as will self-reported adherence over the previous 3 and 30 days. The Urine samples will be collected at every visit for participants in both arms, but stored only for participants in the standard-of-care arm (to be tested locally, in batches by laboratory staff not involved in daily study conduct). Urine samples will only be tested via the tenofovir assay in real-time for participants in the intervention arm by laboratory staff at the Thika Clinic. The results of the urine assay for intervention arm participants will then be recorded by the laboratory staff and conveyed to the research providers of intervention arm participants who will proceed to immediately provide feedback to participants using counseling guides prepared prior to the trial (and informed by the

results of the formative work to qualitatively assess how to provide supportive counseling message for either yes adherence or no adherence, **Section 3.4**).

Hair samples will be collected at each study visit (months 0, 3, 6, 9 and 12) for storage and testing at the end of the study for all participants. (Please see **Section 3.1** for a discussion of how white-coat adherence patterns can be assessed by collecting both short-term and long-term adherence metrics). Feasibility and acceptability assessments will be conducted at study end for research providers (feasibility) and participants in the intervention arm (acceptability), respectively. Plasma and DBS for TFV and TFV-DP level measurement, respectively, will be collected at each visit in each arm as additional adherence metrics and stored for future analysis in the UCSF Hair Analytical Laboratory (HAL) after seeking independent funding for those concentrations.

Participants will be followed over a 12-month study (baseline visit which is month 0, months 3, 6, 9 and 12) period to assess the study outcome measures. This study will follow all aspects of Kenya's PrEP guidelines, except patients randomized to the intervention arm will receive point-of-care adherence testing by the urine tenofovir assay.

5.3. Location and Setting

The setting is the THIKA Partners in Prevention Research Site and Clinic, [name]. The Thika Clinic serves an urban center about 40 kilometers outside of Nairobi and is a center of excellence for PrEP delivery and research in Kenya. Over the past decade, the Thika clinical team established a multi-disciplinary site focused on HIV-1 and sexually transmitted disease prevention research (more than two dozen projects), and on provision of clinical care (HIV-1 testing, HIV-1 comprehensive care, HIV-1 prevention services). The experienced community outreach team at the Thika site has established successful recruitment strategies for research studies, including collaborating with existing HIV-1 testing centers and community-based mobilization for women to engage in HIV-1 prevention studies. The Thika clinic is a center of excellence for PrEP in Kenya and is leading the training of other clinics as part of Kenya's national PrEP scale-up program.

5.4. Population & Eligibility

The eligibility criteria for this study are the following:

- Female
- Adult, age ≥18 years old
- HIV-1 uninfected based on a negative HIV-1 rapid test
- Not currently enrolled in an HIV-1 prevention clinical trial
 - Not currently in a serodiscordant relationship
 - Already taking PrEP and will be enrolled at the 3-month follow-up visit following PrEP initiation

- Willing to be randomized to point-of-care tenofovir drug testing
 - Willing/able to provide informed consent to participate in the study
 - No contraindication to use of TDF or FTC
 - Note: Women who are pregnant or breastffeeding at screening/enrollment are still eligible

Eligibility criteria are meant to approximate HIV-1 uninfected women at risk who have recently initiated PrEP.

5.5. Services and Intervention

Standard-of-care PrEP arm

Participants will receive HIV-1 counseling, condoms, risk reduction counseling, and syndromic management of sexually transmitted infections according to local guidelines at the baseline enrollment visit and during all follow-up visits. All distribution of PrEP will be done with typical counseling and monitoring during the 12-month study period. The participants in this arm will undergo urine collection for storage only and will NOT receive the point-of-care urine tenofovir assay. Per the standard of care when providing PrEP, creatinine is checked every 6 months, urinalysis every 6 months, and a urine pregnancy test for women is performed as indicated by clinical care.

POC Urine Tenofovir PrEP arm (Intervention)

As with the SOC PrEP arm, participants will receive HIV-1 counseling, condoms, risk reduction counseling, creatinine testing, urinalyses, pregnancy testing, and syndromic management of sexually transmitted infections according to the 2016 Kenya PrEP guidelines (**Table 1**). In addition, participants will have clinic-based point-of-care testing for urine tenofovir performed by the POC urine assay at the baseline visit (month 0) and then at each quarterly visit (month 3, 6, 9, 12) during the 12-month study period. The POC rapid strip test (**Figure 6**) will provide information on YES vs. NO recent PrEP adherence among intervention arm participants.

PrEP medication provision and pharmacy control

Tenofovir disoproxil fumarate (TDF) and emtricitabine (FTC) are reverse transcriptase inhibitors that have been approved for the treatment of HIV-1 infection in humans in Kenya, Uganda, and the United States with other antiretrovirals. A fixed-dose, oral co-formulation of FTC/TDF is used in Kenya for PrEP and provided by the Kenya Ministry of Health as part of PrEP roll-out. This drug is not provided as a study drug, but as part of routine care for the participants in this study.

At Thika, TDF/FTC is stored in accordance with the drug manufacturer's recommendations. The pharmacy and storage facility has locked, climate-controlled environments, with controlled humidity and temperature to remain within limits allowed by the manufacturer for drug storage.

Protocol Version 6.0 November 11, 2021 Page 29 of 93

Dispensing will be sufficient to last until the next visit (e.g. 90 days) with extra pills (20) dispensed to allow for a generous visit window.

747748749

746

Counseling on TDF/FTC, its side effect profile, how to take the medication, what to do if side effects are experienced, and the importance of not sharing medication to optimize potential efficacy is performed routinely at each PrEP visit as per the 2016 Kenya PrEP guidelines.

751752753

754

755

756

757

758

759

760

761

762

763764

765

766

767

768

769

770

750

Point of care urine monitoring test

The point-of-care urine-based adherence test is shown in Figure 6 and will be performed for participants in the intervention arm only (urine will be collected and stored without testing until the end of the study for participants in the standard of care arm). The laboratory staff at the Thika Clinic will be trained in the interpretation of this test. As detailed at length in Section 3.3, this competitive assay demonstrates a colored line in samples negative for tenofovir and no line in samples positive for tenofovir (Figure 6) so the laboratory staff will be carefully trained on the interpretation of the test prior to the start of the trial by the PI of the study, the site PIs, and the laboratory manager of the Thika Clinic. Neither the research provider nor the participant will need to interpret the test. The laboratory technologist on site will aid the provider in urine sample collection, perform the test, interpret the test, mark on the test if it is positive or negative, and deliver the results to the research provider for participants in the intervention arm only. The results will be delivered to the research providers for the intervention arm participants from the trained laboratory staff in the form of "yes" versus "no" for recent adherence to tenofovir. The research providers will then immediately deliver the appropriate messaging and counseling based on the urine test results for participants in the study. Of note, pictures of each urine tenofovir assay for participants in the intervention arm will be uploaded into the research database for quality assurance monitoring. After the picture of the test is uploaded into the research database, the used urine test will be discarded in an appropriate manner.

771772773

774

775

776

777

Feedback to the participants on their tenofovir test results will be delivered in a supportive manner by the research providers. The messages to provide feedback on adherence will be adapted from HPTN082¹⁷⁹ (**Figure 8**), for which [name] serves as co-investigator. The counseling messages for this trial will first be piloted in a small group of women on PrEP at Thika for refinement prior to actual implementation.

Enhanced adherence counseling (EAC) to the women in the intervention arm will be delivered by healthcare providers at the Thika Clinic (nurses, doctors, clinical psychologist) with extensive experience in counseling and behavioral interventions. When asking about particular barriers and

778

779

780

781

782

783

784

785

786

787

788

789

790

791

792

793794

795

796

797

798

799

800

801 802

803

804

805

806

807

808 809

810

811

812

813

Figure 8: Counseling messages to be delivered based on urine TFV results in real-time in intervention arm (based on HPTN082, *adapted with permission*)

Urine test positive	Key message: You are doing really well! You are taking the PrEP. Keep up the good work and remember that taking one PrEP pill every day is needed for strong protection against HIV.
Urine test negative	Key message: It looks like you haven't been able to take the PrEP pills, at least recently. Are you still interested in PrEP? If yes, how can we help you take the medication? Talk to us about what makes it hard to take and let us see how we can help

ways the Thika clinic providers can help in supporting the participant in adherence, counseling messages during EAC will be tailored to the individual's circumstances.

Both study arms

For retention efforts in the study, participants will be contacted every 3 months if they do not appear for their quarterly PrEP visits for follow-up of safety issues, HIV-1 assessment, PrEP refills, and to ask if they want to continue participation in the study. Moreover, all participants will be contacted at the end of the study (even if they did not participate in all study visits) to obtain hair samples for measurement of long-term PrEP adherence and for acceptability interviews if applicable.

5.6. Recruitment and Enrollment

The Thika site has established local recruitment and screening methods that operationalize protocol-specified requirements for eligibility determination in a manner that is tailored to and most efficient for the local study setting and target study population. To reduce any bias towards participants who might be more adherent to PrEP or be amenable to adherence testing, enrollment will target areas with low PrEP uptake.

Recruitment strategies will include partnering with existing voluntary counseling and testing (VCT) centers, outreach workers and community organizations, such as churches, and community mobilization around women's VCT promotion. Recruitment materials will educate women about PrEP. Screening and enrollment may occur on the same day or may be split across days, depending on the preferences of the potential participant. Informed consent for study participation and enrollment in the study may proceed on the same day when eligibility is determined.

A member of the study team will approach individuals within the PrEP clinic at the Thika Clinical research site and at community sites associated with Thika at their 3 month routine follow-up visit

814815816

817

following PrEP initiation. They will describe the study and ask for voluntary participation. They will explain the purpose of the study and review the study eligibility criteria with the participant. They will also address any questions about study participation. The eligible adults interested in participating in the study will be asked to sign the informed consent form to participate (see Appendix I). Those people who decide not to participate in the study will experience no detrimental impact on their routine care at the clinic. Those who want to voluntarily participate will be taken to a private area of the clinic to be asked several demographic and clinical questions.

The major talking points will be the following:

- The study is for HIV-uninfected women who recently initiated PrEP.
- The purpose of the study is to investigate whether feedback of urine drug levels may help improve long-term adherence to PrEP.
- If adherence to PrEP is very good, then you will have a lower chance of becoming infected with HIV.
- If you are eligible to participate in the study, then the study team will randomly assign you by chance (like a coin flip) to either the "regular care group" or the "intervention group." If you are in the "regular care group", then you will receive all the same treatment that you would normally receive, including the HIV medications for PrEP. If you are in the "intervention group", then you will receive all the same treatment that you would normally receive, including HIV medications for PrEP but in addition, you will have PrEP drug level testing every three months with a simple urine dipstick test.

After enrollment, the participant will be randomized to either the control arm or the intervention arm in a 1:1 fashion.

5.7. Randomization

The study design will be an open-label, randomized, implementation trial with 2 study arms. We will enroll healthy HIV-uninfected adults (≥18 years old). We will enroll a minimum of 100 and not exceeding 120 women receiving PrEP, about 50 - 60 participants in each study arm.

Randomization will be done in variable-sized blocks using opaque envelopes opened at the time of randomization. Randomization will occur in a 1:1 fashion to alternate the intervention arm and the standard of care arm. Randomization will be done at the enrollment visit.

The allocation of participants for the 2 study arms will be the following:

	Standard of Care Arm	Intervention Arm	Total
Total	50 - 60	50 - 60	100 - 120

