5.8. General Study Procedures

Specific study procedures will take place at screening and enrollment, and then quarterly for both the standard-of-care arm as well as the intervention arm for up to 12 months. At screening, eligibility information will be collected. Subjects who meet the eligibility criteria will then be enrolled in the study.

Once written consent is obtained, a member of the study team will collect demographic and health questions, related to age, birthdate, income, employment history, prior HIV testing, medical conditions, and current symptoms. They will also obtain each participant's phone number, address, and relevant contact information. After obtaining the baseline demographic and clinical data, they will determine the study group randomization of the participant.

A Research Nurse will then meet the participant in the same clinical exam room, and administer a brief clinical questionnaire. The nurse will coordinate the necessary blood draws for the participant, so each participant will only have one blood draw for each clinical visit. As part of PrEP initiation, several standard of care laboratory tests would have been completed prior to trial entry including HIV-1 testing, serum creatinine, Hepatitis B surface antigen, urine pregnancy test. For this study, additional information will be collected on medical history, physical exam findings, and STI syndromic assessment and additional testing will be done as part of standard of care PrEP follow-up.

PrEP delivery will be according to the 2016 Kenya PrEP guidelines, including measurement of renal function (estimated creatinine clearance >60 mL/min to start PrEP and periodic monitoring over time, aligned to the visit schedule of the study), standard clinical assessment to avoid continuing PrEP during acute HIV-1 infection, and adherence counseling. Subjects will then be randomized at enrollment (Month 0 but the 3—month visit on PrEP) in a 1:1 fashion, as described above. Participants in either arm will be provided 3 months of PrEP medication, corresponding to enough to last until the next clinic-based visit. Participants in both arms will be counseled on PrEP discontinuation according to Kenya national guidelines.

At each study visit, we will offer counseling for participants for HIV-1 testing (pre- and post-testing), HIV-1 infection risk reduction best practices, condom promotion and provision, adherence to PrEP medication, as well as other HIV-1 prevention strategies.

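### Section 5.7 gives two incompatible allocation rules in adjacent sentences, variable-sized blocks and alternation, and nothing in the protocol corrects the second

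*Combined protocol and SAP*

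**What the plan says.** Section 5.7 describes the design: "The study design will be an open-label, randomized, implementation trial with 2 study arms". It then gives the allocation method: "Randomization will be done in variable-sized blocks using opaque envelopes opened at the time of randomization". The next sentence reads: "Randomization will occur in a 1:1 fashion to alternate the intervention arm and the standard of care arm". Block sizes are not stated.

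Other sections touch on allocation as follows.

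- Section 5.2 has women randomized 1:1 "using sealed opaque envelopes to the intervention arm versus the SOC arm".
- Section 5.6 has staff tell women that "the study team will randomly assign you by chance (like a coin flip".
- Section 5.8 says that, once consent and baseline demographic and clinical data are in hand, members of the study team act: "they will determine the study group randomization of the participant". It repeats the 1:1 ratio and refers back to the earlier description for the method.
- Section 5.3 describes one study site: "The setting is the THIKA Partners in Prevention Research Site and Clinic".

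No other section mentions alternation, and none says which of the two sentences in Section 5.7 governs.

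**The concern.** Alternation is a fixed sequence. Once one assignment is known, so are all the later ones, and an opaque envelope conceals nothing. In an open-label trial at one site, the last assignment is not hidden from staff.

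Section 5.6 adds opportunity. Screening and enrolment may fall on one day or be split across days, and "Informed consent for study participation and enrollment in the study may proceed on the same day when eligibility is determined". Someone who knows the next arm could encourage one woman and defer another. Because women are approached at their 3-month PrEP visit, the clinic may already have an impression of how well they take the drug.

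The exposed result is the between-arm comparison of hair tenofovir, which Section 6.1 lists among the three primary outcomes and Section 6.4 tests at month 12. Adherence is exactly what that comparison measures. Adjusting for baseline hair level and the listed covariates removes only the part of any selection that those variables capture.

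**Working it through.** **The plan's own figures.** Section 6.3 uses an SD of 1.2 for the change in log hair tenofovir, 50 women per arm and a 0.05 level (taken as two-sided). It gives detectable differences of 0.68 (80% power) and 0.79 (90% power). The two-sample t-test returns 0.679 and 0.786, and power at the stated differences is 0.801 and 0.903. Fold changes are exp(0.68) = 1.97 and exp(0.79) = 2.20. These figures reproduce, and none depends on how the sequence is generated.

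**Can the two rules coexist?** Take a block of 4 as an illustration. It has 4!/(2!·2!) = 6 balanced orders, of which only 2 alternate (ABAB and BABA). An alternating sequence can be cut into balanced blocks, but only by fixing the order within each one, and that removes the randomness. Alternation keeps the 1:1 ratio and discards the random order.

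**Predictability under alternation.** The first assignment is a coin toss and the rest are certain:

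- N = 100: (0.5 + 99)/100 = 99.5% correct guesses
- N = 120: (0.5 + 119)/120 = 99.6%

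**Predictability under permuted blocks.** Suppose a guesser knows all past assignments but not the block sizes, and always names the arm that is behind, tossing a coin when the arms are level. In a block of size 2m the expected number of correct guesses is m + 2^(2m−1)/C(2m, m) − 1/2.

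| Block size | Expected correct | Share |
|---|---|---|
| 2 | 1 + 2/2 − 0.5 = 1.500 | 75.0% |
| 4 | 2 + 8/6 − 0.5 = 2.833 | 70.8% |
| 6 | 3 + 32/20 − 0.5 = 4.100 | 68.3% |
| 8 | 4 + 128/70 − 0.5 = 5.329 | 66.6% |

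For sizes mixed with equal probability, the share is total expected correct divided by total size:

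- 2 and 4: (1.500 + 2.833)/6 = 72.2%
- 2, 4 and 6: (1.500 + 2.833 + 4.100)/12 = 70.3%
- 4 and 6: (2.833 + 4.100)/10 = 69.3%
- 4, 6 and 8: (2.833 + 4.100 + 5.329)/18 = 68.1%

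Simulation over 100 and 120 assignments gives about 72%, 70%, 69% and 68% in the same order. All these block sizes are assumptions. Independent coin tosses would give 50%.

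**The case against.** The strongest reply is that one verb stands against everything else. The challenged sentence itself begins by calling the process randomization. Variable blocks and opaque envelopes would serve no purpose under alternation, and telling women that assignment is by chance would be untrue. The natural reading is that the author meant 1:1 balance. That stands, and it limits the point to a contradiction in the text.

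Several stronger inferences are tempting, and the documents do not support them.

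- *That alternation was used, or that 99 to 119 of the 100 to 120 women were enrolled with their arm known.* Those counts are the ceiling under the literal reading. Nothing shows that it was followed.
- *That retention and acceptability are biased between arms.* Section 6.4 describes 12-month retention as a proportion with a confidence interval, with no arm comparison stated. Section 5.2 places the acceptability assessment in the intervention arm only.
- *That envelopes are opened too early.* Sections 5.6 to 5.8 already put consent and baseline demographic and clinical data before assignment. This order protects concealment only if the sequence is unpredictable.
- *That staff necessarily hold pill counts and self-reported adherence when they assign.* Section 5.8 does not list these among the items collected before assignment.

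Two further points soften the risk. Women are also approached at community sites linked to Thika, so a recruiter would need to know the last assignment made elsewhere. And Section 6.3 says that statistical significance on the hair outcome is not the aim of this pilot. Neither removes the conflict: the hair comparison remains a primary outcome, and Section 5.7 is the only section that defines the sequence.

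**Conclusion.** The contradiction is real and sits in the operative section. The likely explanation is loose wording, but the text alone does not tell site staff or a later reader which rule applies.

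Read literally, it raises predictability from roughly 67-72% correct guesses to near-complete knowledge of the sequence. The lower range assumes block sizes of 4, 6 or 8, or mixtures that also include 2. The upper figure assumes that staff know the previous assignment. The documents give no basis for estimating the resulting bias in log hair tenofovir, so none is offered. Even with blocks alone, some predictability remains in an open-label trial at one site.

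**What to change.** In Section 5.7, delete the words from *to alternate* to the end of the sentence, so that it stops after *1:1 fashion*. Randomly permuted, variable-sized blocks in sealed opaque envelopes then stand as the only allocation rule, in line with Section 5.2.

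If enrolment has begun, check the allocation list against the order of enrolment and record in the trial file which method was used.

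The cost is one deleted phrase and, if needed, one look at an existing list. Naming who generates the sequence and whether envelopes are numbered would add useful detail, but the contradiction can be resolved without it.
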